Palbociclib was approved for use as first-line treatment of HR+/HER2- advanced BC in postmenopausal women, based on the phase II study Palbociclib Ongoing Trials in the Management of BC (PALOMA) PALOMA-1(13) and the phase III study PALOMA-2 (10). Palbociclib was approved for use with fulvestrant as second- or later-line treatment of HR+/HER2- advanced BC based on the phase III study PALOMA-3 (14,15). In PALOMA-1, median PFS was 20.2 months for the palbociclib-letrazole group versus 10.2 months for the placebo-letrazole group (hazard ratio [HR] for risk of progressing: 0.488, 95% confidence interval 0.319-0.748) (13); and In PALOMA-2, it was respectively 24.8 months versus 14.5 months (hazard ratio 0.58; 0.46 to 0.72) (10). In PALOMA-3, median PFS was 9.5 months in the palbociclib-fulvestrant group versus 4.6 months in the placebo-fulvestrant (hazard ratio (HR): 0.46, 0.36-0.59)(14); and specifically for patients with prior resistance to hormonal therapy and visceral metastases, it was respectively 9.2 months versus 3.4 (HR, 0.47; 0.35-0.61) (15).

Palbociclib was recommended for use with an aromatase inhibitor in patients with locally advanced and MBC in the NHS in England by NICE in November 2017 and by the SMC in December 2017 (16,17). In order to provide access to palbociclib in the UK during the

NICE/SMC appraisal period, the IPP was run by Pfizer between April 2017 and November 2017 for England and Wales, and December 2017 for Scotland. The IPP provided free access to treatment to NHS patients with previously untreated (or >12 month since discontinuation of adjuvant or neoadjuvant treatment with a nonsteroidal aromatase inhibitor), HR+/HER2-MBC (18).

Palbociclib and other CDK4/6 inhibitors have been generally well tolerated by patients. Based on pooled data from 3 randomised studies in patients who received palbociclib in combination with endocrine therapy (N=872), one most common side effect has been neutropenia soon after initiation of therapy which affects 80.6% of patients, including 10.1% experiencing grade 4 neutropenia and 1.6% experiencing febrile neutropenia (19). Palbociclib-induced neutropenia has also been shown to reverse rapidly with dose interruption and/or dose reduction (11).

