5.1 FULL ANALYSIS SET

The full analysis set will be comprised of medical records extracted for the purpose of the study from all eligible patients who are enrolled into the study (either deceased with access to their medical records via their direct care team or living and having provided written informed consent to access of their medical records as part of the study). Analysis will be conducted on the 2-year follow-up data.

PFIZER CONFIDENTIAL

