Secondary Objective 2: To describe overall survival and progression-free survival, response (CR, PR), stable disease. This includes estimating the proportion of patients achieving those endpoints at 1, 2 and 3 years following palbociclib initiation; median survival, time to response and duration of response. In patients who respond to treatment, to describe PR and CR using "swimmer plots".

- Proportion of patients at 2-years following initiation of palbociclib who:
 - Are free from disease progression.
 - Are alive
 - Achieved PR
 - Achieved CR
 - Had stable disease
- Median (95% confidence interval [CI]):
 - PFS

PFIZER CONFIDENTIAL

- OS
 - Time to achieving best overall response
- Length of follow-up
- Best response to palbociclib, overall and by de novo and relapse status
- Time to best response – by de novo and relapse status
- Time to first response – overall and by de novo and relapse status

Secondary Objective 3: To describe the occurrence of neutropenia during the first-year post-initiation observation period.

- In the 6 months post-palbociclib initiation, proportion of patients who experience,
 - Neutropenia (overall and by grade, recorded and inferred from ANC measurements).
 - Worst neutropenia experienced within 3 months of palbo initiation
 - Febrile Neutropenia.

[figure not shown]
Secondary Objective 4: To describe the occurrence of gastro-intestinal toxicity, including diarrhoea, nausea and vomiting during the first-year post-initiation observation period.

- For each cycle, proportion of patients who experience Gastro-intestinal toxicity, including:
 - Diarrhoea.
 - Severity
 - Nausea.
 - Severity
 - Vomiting.
 - Severity
- Proportion of patients experiencing an AE during follow-up

Secondary Objective 5: To describe progression of clinical indicators, including biochemical and radiological indicators at each time-point available during the first year following palbociclib treatment initiation.

- Summary measures of full blood counts in the first 6 months following initiation:
 - Haemoglobin.
 - White cell counts.
 - Absolute neutrophil counts.
 - Platelet counts.
- Summary measures of liver function tests in the first 6 months following initiation:
 - aspartate transaminase (also called aspartate aminotransferase).
 - alanine transaminase (also called alanine aminotransferase).
 - alkaline phosphatase.
 - Albumin
 - Bilirubin

PFIZER CONFIDENTIAL

[figure not shown]

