8 STATISTICAL METHODOLOGY AND STATISTICAL ANALYSES

8.1 STATISTICAL METHODS

[figure not shown]
The following statistical methods will be used:

Full analysis will be conducted on 2-year follow up data not 3-year follow up data.

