8.2 STATISTICAL ANALYSES

Definitions will be implemented as in section 8.1.3. Patients who are known to be alive at the date of data collection (1-year for interim report and 3-year for full study report) will be censored at the date of data collection, and patients who are lost to follow-up will be censored on the date they were last known to be alive (e.g., date of last recorded hospital visit). Patients who are alive and free from disease progression at the date of data collection and those lost to follow-up will be censored on the date they were last known not to have disease progression (i.e., the date of last documented response assessment). Patients remaining in CR or PR at the end of the post-initiation observation period or lost to follow-up will be censored on the date CR or PR was last documented.

[figure not shown]
[figure not shown]
Note: Some analyses that were originally proposed were not conducted as per the decisions of the CI and Pfizer team, these have been kept in this section as a record.

8.2.1 Primary Objective: To describe patient demographic and clinical characteristics at initiation of palbociclib.

Proposed: Age, duration of MBC prior to palbociclib (calculated by subtracting the date of initial BC diagnosis from the date of palbociclib initiation), number of lymph nodes involved, tumour size at initial disease diagnosis and Ki67 values will be summarised as quantitative variables (see section 8.1.1) using measures of central tendency (mean and median) and dispersion (standard deviation, interquartile range [IQR] and range) will be calculated. All other variables analysed as part of the primary endpoint, whether categorical or binary, will be presented as frequencies and percentages.

Actual: Age was presented as both a quantitative variable as per section 8.1.1 and as a categorical variable (Categories: Less than 40 years old, between 40 and 50 years old,

PFIZER CONFIDENTIAL

[figure not shown]

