prescribed treatment in the 1st, 2nd, and 3rd line after palbociclib discontinuation was presented as a categoric variable as per section 8.1.2. Dose, duration of subsequent treatments and number of completed 28-day cycles per patient were presented as quantitative variables as per section 8.1.1. Number of completed 28-day cycles (categories: 1-6 cycles, 7-12 cycles, 13-18 cycles, 19-24 cycles, 25-27 cycles and No completed cycles) and the proportion of patients co-administered letrozole or fulvestrant were presented as categoric variables as per section 8.1.2. All other endpoints were evaluated as proposed.

8.2.3 Secondary Objective 2: To describe overall survival and progression-free survival, response (CR, PR), stable disease. This includes estimating the proportion of patients achieving those endpoints at 1 and 2 following palbociclib initiation: median survival, time to response and duration of response. In patients who respond to treatment, to describe PR and CR using “swimmer plots”.

Proposed: For the estimation of the proportion of patients alive, and free from disease progression, the denominator will be all patients known to be alive at the selected time-points (e.g., 1 years, 2 years, and 3 years). For the estimation of the proportion of patients achieving PR, CR and with stable disease at the selected time-points (1 years and 2 years), the denominator will be all patients with at least one assessment of response (CR / PR / no response or stable disease / progressive disease) in the past year.

[figure not shown]
Actual: Proportion of patients free from disease progression, are alive, achieved PR, CR or stable disease were analysed separately at the 2-year timepoint only. Length of follow-up, and time to best response and first response were presented as quantitative variables as per section 8.1.1. Best response to palbociclib, overall and by de novo and relapse status was treated as a categoric variable and analysed according to section 8.1.2.

8.2.4 Secondary Objective 3: To describe the occurrence of neutropenia during the first-year post-initiation observation period.

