Describing treatment patterns 1,2 and 3 years after palbociclib initiation	Full Analysis set	Secondary Objective 1	Overall and Treatment Line	Frequency tables and percentages for proportions of patients completing a 28-day cycle, co-administered letrozole and fulvestrant at palbociclib initiation. Summary statistics calculated (incl. Mean/Median/SD/IQR/Range) for number of completed 28-day cycles	Excluded
Proportion of patients free from disease progression	Full Analysis set	Secondary Objective 2	Overall and Treatment Line	Frequency tables and percentages	Excluded
Proportion of patients alive	Full Analysis set	Secondary Objective 2	Overall and Treatment Line	Frequency tables and percentages	Excluded
Proportion of patients achieving PR/CR/with stable disease	Full Analysis set	Secondary Objective 2	Overall and Treatment Line	Frequency tables and percentages	Excluded
Median PFS	Full Analysis set	Secondary Objective 2	Overall and Treatment Line	Kaplan-Meier analysis, median PFS measured as being time from the date of palbociclib initiation to the date of first document disease progression or death. 95% confidence intervals calculated for median.	Standard imputation for dates (section 7), otherwise exclude.
Median OS	Full Analysis set	Secondary Objective 2	Overall and Treatment Line	Kaplan-Meier analysis, median OS measured as being time from the date of palbociclib initiation to the date of death. 95% confidence intervals calculated for median.	Standard imputation for dates (section 7), otherwise exclude.
Median time to best overall response (CR or PR)	Full Analysis set	Secondary Objective 2	Overall and Treatment Line	Kaplan-Meier analysis, time to first best overall response (partial/complete response) measured as being time from the date of palbociclib initiation to the date of first response. 95% confidence intervals calculated for median.	Standard imputation for dates (section 7), otherwise exclude.
Swimmer plots	Full Analysis set	Secondary Objective 2	Overall and Treatment Line	Swimmer plots used to represent patient response (CR / PR/ stable disease / progressive disease) to treatment for patients responding to treatment (CR or PR).	
Duration of response (PR/CR)	Patients enrolled achieving PR/CR	Secondary objective 2	Overall and Treatment Line	Kaplan-Meier analysis, median duration of response measured as being time from the	Standard imputation for dates (section 7),

PFIZER CONFIDENTIAL

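### With the final analysis cut to 2-year data, the first-line PFS median falls at the edge of follow-up, and the SAP commits to no sound summary if a survival median or its upper limit is not reached

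*SAP*

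**What the plan says.** SAP 8.1 sets the horizon: "Full analysis will be conducted on 2-year follow up data not 3-year follow up data". SAP 5.1 repeats it for the full analysis set: "Analysis will be conducted on the 2-year follow-up data". Two other places do not fit a clean 24-month cut. The censoring rule in SAP 8.2 still reads "Patients who are known to be alive at the date of data collection (1-year for interim report and 3-year for full study report", and the cycle categories reported under Secondary Objective 1 end with "25-27 cycles and No completed cycles".

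For Secondary Objective 2, SAP 6 lists "Median (95% confidence interval [CI" for PFS and OS. SAP 8.2.9 gives Kaplan-Meier analysis for both, overall and by treatment line, with "95% confidence intervals calculated for median". Nothing says what is reported if the curve or its confidence band does not cross 50%.

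SAP 6 also lists the proportions progression-free and alive at 2 years. SAP 8.2.3 (and Protocol 9.7) takes patients known to be alive at the time point as their denominator. SAP 8.2.9 gives them frequency tables and percentages with no interval. SAP 8.1.3 permits Kaplan-Meier proportions but does not require them.

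Protocol 7 supplies the first-line references: 20.2 months in the phase II study and, for the phase III study, "In PALOMA-2, it was respectively 24.8 months versus 14.5 months (hazard ratio 0.58; 0.46 to 0.72".

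**The concern.** A Kaplan-Meier median exists only if the curve falls to 50% within follow-up, and its upper limit only if the upper confidence band does too. The protocol planned 3 years, which leaves room beyond both first-line reference medians. The SAP shortened the data to 2 years and kept the median with a two-sided interval as the survival summary.

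Median survival is a named part of Secondary Objective 2. At stake is whether the first-line PFS result, and possibly the OS result, comes out as a complete estimate or as an open-ended one, with no agreed summary to report in its place.

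**Working it through.** The plan gives no figure to reproduce: the study is descriptive with no hypothesis (SAP 4.1), and its size was chosen pragmatically (Protocol 9.5).

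**Inputs.**
- Horizon: 24 months (SAP 5.1, 8.1).
- First-line median PFS: 20.2 or 24.8 months. Second- or later-line: 9.5 months (Protocol 7).
- Patients: about 200 (SAP 2.1) or 250 (SAP 5). The first-line number is not given, so 100 to 250 is assumed.
- Assumed: exponential times, no dropout. As a check, exponential times imply a hazard ratio equal to the ratio of medians: 14.5/24.8 = 0.585 against the stated 0.58, and 10.2/20.2 = 0.505 against 0.488.

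**PFS at 24 months.** S(24) = 0.5^(24/median).
- Median 20.2: S(24) = 0.439.
- Median 24.8: S(24) = 0.511.

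**Chance the median is reached.** Without dropout this is P(events ≥ n/2), with events binomial(n, 1 − S(24)).

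**Chance the upper limit is reached.** The log-log Brookmeyer-Crowley upper band at 24 months must be at or below 0.5. At n = 200 this needs 114 events, where S = 0.43:
- standard error of log(−log S) = √(114/(200×86)) / |ln 0.43| = 0.0814/0.844 = 0.0965;
- upper band = 0.43^exp(−1.96×0.0965) = 0.497.

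The chance of 114 or more events is 43% at the 20.2-month reference and 1.3% at 24.8.

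| n | Reached, 20.2 | Upper limit missing, 20.2 | Reached, 24.8 | Upper limit missing, 24.8 |
|---|---|---|---|---|
| 100 | 91% | 75% | 45% | 98% |
| 150 | 94% | 65% | 42% | 99% |
| 200 | 97% | 57% | 40% | 99% |
| 250 | 98% | 51% | 38% | 99% |

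**Sensitivity (n = 200).**
- Weibull shape 0.8 to 1.2, or 10% loss to follow-up: median reached in 91-99% (20.2) and 37-43% (24.8).
- Follow-up to 27 cycles (27 × 28 = 756 days = 24.8 months): the 24.8 case rises to 53-55% reached. At 28 months it is 90%.
- At 36 months, the protocol's horizon: median reached in about 100% under either reference, upper limit in 97% or more.
- Censoring PFS at the last assessment (SAP 8.2), with assumed staggered scans every 3-4 months: at 24.8 the median is reached in about 84-93%, with the upper limit missing in 64-81%; at 20.2 the upper limit is missing in 17-36%. The rise comes largely from the risk set emptying in the last scan interval, so a median read there may be an artefact.

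**OS at 24 months (n = 200, same formula).**
- Assumed true median 28, 30 or 36 months: reached in about 8%, 2% and 0%.
- The only survival figures in the documents are for stage IV breast cancer generally: 63% at 1 year and 15% at 5 years (Protocol 7). They imply medians of 12·ln 2/(−ln 0.63) = 18.0 and 60·ln 2/(−ln 0.15) = 21.9 months, reached in over 99% and 83%.

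**A summary that always exists.** For the 24.8-month reference, λ = ln 2/24.8 = 0.02795.
- 24-month restricted mean = (1 − 0.511)/0.02795 = 17.5 months.
- SD of min(T, 24) = 8.2, so SE = 8.2/√200 = 0.58 and the 95% CI is ±1.1 months.
- 24-month proportion: ±1.96·√(0.511×0.489/200) = ±6.9 percentage points.

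**The case against.** The strongest reply has five parts.

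- **Other summaries are planned.** The 2-year proportions are there, so it would be wrong to say that nothing is. They are not a sound substitute. With patients known to be alive as the denominator, the proportion alive is 100% by construction and the progression-free proportion is conditional on survival. No interval is given, and the Kaplan-Meier version is optional.
- **The result depends on the reference.** A reader might infer that the first-line PFS median probably cannot be estimated. That holds only at 24.8 months; at 20.2 the median is usually reached. This part stands.
- **OS.** A reader might also infer that median OS will almost surely be out of reach. The documents do not support that. OS cannot be shorter than PFS as defined, and Protocol 7 ties the low survival rates to the time before palbociclib, but the only survival figures given, from a broader population, point to 18-22 months. This part stands too.
- **The cohort is mixed and the cut unclear.** If 5%, 10% or 20% of patients (assumed shares) are later-line with a 9.5-month median, S(24) = 0.174 for them and the overall S(24) is 0.494, 0.478 or 0.444. The overall PFS median is then reached in 59%, 76% or 95% of studies at n = 200, even with 24.8 months for the rest. This helps the overall estimate, not the first-line one. A cut slightly after 24 months also helps, and the SAP leaves that open.
- **An unreached median is a valid result in a descriptive study.** True, and SAP 8.2 already records many analyses as done. But the SAP has no reporting rule for that outcome, and the data for a better summary are in hand.

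**Conclusion.** The point holds in a limited form. Cutting the analysis to 2 years puts the first-line PFS median at the edge of follow-up. At a strict 24-month cut with exponential times and no dropout, the median with a complete two-sided interval is more likely than not incomplete under either protocol reference: the upper limit is missing in about 51-75% of studies at 20.2 months and 98-99% at 24.8. The point estimate is likely at the first reference (91-98%) and less likely than not at the second (38-45%). At 20.2 months the result is sensitive: censoring at the last assessment, or a slightly later cut, makes a finite upper limit more likely than not.

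Median OS may or may not be reached, from about 0-8% for assumed medians of 28-36 months to over 80% for 18-22 months. Nothing in the documents justifies a firmer statement. Second- or later-line PFS is not affected: at a 9.5-month median the curve crosses 50% well inside 24 months.

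The gap is that the SAP neither says how an unreached median is reported nor commits to a fixed-horizon summary in all patients with an interval.

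**What to change.** In SAP 6, 8.1.3 and 8.2.9, commit to a fixed-horizon Kaplan-Meier summary of PFS and OS in all patients, overall and by treatment line:

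- the 24-month restricted mean with 95% CI;
- the 24-month Kaplan-Meier proportion with 95% CI beside it, with numbers at risk shown, because censoring at the last assessment thins the risk set there;
- the median where it is reached, and otherwise a statement that it was not reached, with its lower 95% limit.

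Reconcile the horizon in SAP 8.1 with the 3-year censoring wording in SAP 8.2, and state whether 2-year data means truncation at 24 months from the index date or a data-collection round that may run later.

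The cost is SAP wording and a small amount of extra analysis on data already collected; where results have been produced, these summaries should be labelled as added. Restricted means are less familiar than medians, and the protocol's benchmarks are medians, so the median stays alongside.

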8.1.1 Analysis for quantitative data

Quantitative data will generally be analysed using basic summary statistics of central tendency (including means and medians) and dispersion (including standard deviations, the interquartile range [IQR] and the range). If distributions are normally distributed (evaluated through inspection of histograms), 95% confidence intervals will be calculated assuming a normal distribution, otherwise the median and IQR will be presented instead. Where appropriate, i.e., for ordinal endpoints frequency and percentages will be presented along with summary statistics.

PFIZER CONFIDENTIAL

8.1.2 Analysis for categorical data

For categorical data, frequency and percentage tables will be presented.

8.1.3 Analysis for binary endpoints

Most binary endpoints will be summarised using frequency tables with percentages. For survival-related endpoints, Kaplan-Meier analysis may be used with proportions of patients reaching an event after different time periods and median survival (the time at which 50% of patients have reached a given endpoint out of all patients that are still being followed-up at that point or have reached that given end point) with 95% confidence intervals estimated using the method of Brookmeyer and Crowley⁶ or another appropriate method⁷. Swimmer plots will be used to show individual patient response to treatment over time (CR, PR, stable disease, progressive disease); these are plots that display a range of information with bars indicating the length of follow-up for each individual patient and symbols on the bars showing where CR and PR are reached and end.

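### SAP 8.1.3 describes the median in words that leave out patients censored earlier; this is not the Kaplan-Meier median the plan names and, taken literally, can only be equal or shorter

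*SAP*

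**What the plan says.** SAP 8.1.3 states: "For survival-related endpoints, Kaplan-Meier analysis may be used with proportions of patients reaching an event after different time periods". It adds median survival with 95% limits "estimated using the method of Brookmeyer and Crowley" or another suitable method. A bracket in the same sentence explains the median as "the time at which 50% of patients have reached a given endpoint out of all patients that are still being followed-up at that point", continuing "or have reached that given end point".

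SAP 8.2 then opens with "Definitions will be implemented as in section 8.1.3". Its censoring rules follow: "patients who are lost to follow-up will be censored on the date they were last known to be alive", and for PFS, patients without progression are censored at their last documented response assessment. SAP 8.1 limits the full analysis to 2 years of follow-up.

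Other places name the estimator without a bracket. The SAP 8.2.9 table lists Kaplan-Meier for median PFS, median OS, time to best response and duration of response. Protocol 9.7 says that medians for PFS, OS, time to best response, time to dose modification and time to discontinuation will come from Kaplan-Meier curves.

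For the treatment endpoints the SAP differs from the protocol:
- Section 6 restricts time to discontinuation to patients who stopped permanently, and time to dose reduction to the first-line group.
- Section 8.2.2 (Proposed) and the 8.2.9 table summarise both times with means, medians and ranges.
- Section 8.2.2 (Actual) groups time to dose reduction into categories.

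**The concern.** The bracket's denominator is events so far plus patients still followed. Someone censored at month 10 counts in neither group at month 18, whereas Kaplan-Meier uses that patient's 10 event-free months. All earlier events stay in while part of the event-free experience is removed, so the event fraction is too high once anyone has been censored.

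The bracket is the only place where the SAP says what the median is, SAP 8.2 refers back to that section for definitions, and the commitment to Kaplan-Meier there is permissive: "For survival-related endpoints, Kaplan-Meier analysis may be used". The plan therefore holds two rules for the same number. A programmer or reader who followed the wording would report medians for PFS, OS and duration of response that are too short and that do not match the Brookmeyer-Crowley interval beside them.

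**Working it through.** The study is descriptive and states no planned median, so there is no figure of the plan's own to reproduce. The check compares the two definitions.

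**Notation.** Of n patients, by time t: D have the event, R are still followed, C were censored, so n = D + R + C. S is the Kaplan-Meier estimate.
- Bracket: first t with D/(D + R) ≥ 0.5.
- Kaplan-Meier: first t with S ≤ 0.5.

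**Small example.** Ten patients: 4 progress by month 12, 2 are censored at month 13, 4 remain. Kaplan-Meier stays at 6/10 = 60% progression-free. The bracket gives 4/(4 + 4) = 50%, so the median is declared reached at month 13, on a censoring date with no event.

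**Direction.** Kaplan-Meier passes the weight of each patient censored at time c to those who remain:

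n·S(t) = R + Σ S(t)/S(c) ≥ R + C·S(t), because S(c) ≤ 1.

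Hence (n − C)·S ≥ R, and since n − C = D + R, S ≥ R/(D + R). The bracket's event fraction is never below 1 − S, so its median is never later than the Kaplan-Meier median. The two agree if no one is censored before the median.

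**Size.** Inputs:
- True medians of 20.2 and 24.8 months. These are the palbociclib arms of the two first-line trials cited in Protocol section 7, used for illustration only.
- Exponential event times, rate λ = ln 2/median (assumption).
- Exponential early censoring, rate c = −ln(1 − annual loss)/12, at 0% to 20% per year (assumption; the documents give no rate).

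With r = λ/(λ + c), the expected D equals R when exp(−(λ + c)t) = r/(1 + r), so the bracket's median is r·ln(1 + 1/r)/λ.

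Example, 24.8 months and 10% per year: λ = 0.02795, c = 0.00878, r = 0.761, and 0.761 × 0.839/0.02795 = 22.8 months.

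| Annual loss | True 20.2 | Change | True 24.8 | Change |
|---|---|---|---|---|
| 0% | 20.2 | 0 | 24.8 | 0 |
| 5% | 19.5 | −3.3% | 23.8 | −4.0% |
| 10% | 18.9 | −6.5% | 22.8 | −7.9% |
| 20% | 17.6 | −12.7% | 21.1 | −15.1% |

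**Two-year cut.** Simulation with N = 200 (the SAP's approximate number), 1,000 runs per case, follow-up ending at 24 months. Share of runs in which the median is not reached:

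| True median | Annual loss | Kaplan-Meier | Bracket |
|---|---|---|---|
| 24.8 | 10% | 61% | 29% |
| 24.8 | 20% | 62% | 9% |
| 20.2 | 10% | 5% | 0.5% |
| 20.2 | 20% | 6% | 0% |

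The inequality held in every simulated dataset.

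**Treatment endpoints.** The bracket does not govern these, because SAP 8.2.2 sends them to the 8.1.1 summaries. Their problem is the restriction to patients with the event. In a 2-year analysis, a median among those who stopped cannot exceed 24 months. For illustration, assume stopping times are exponential with median 20.2 months and everyone is followed for 24 months. A fraction 1 − 2^(−24/20.2) = 0.561 stop, and the median among them solves 1 − 2^(−t/20.2) = 0.561/2, so t = 9.6 months. With a true median of 24.8 months the same steps give 10.0 months.

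**The case against.** The strongest reply is that the bracket is a loose gloss and the method is already fixed. The same sentence names Kaplan-Meier and Brookmeyer-Crowley, the 8.2.9 table lists Kaplan-Meier without *may*, Protocol 9.7 says it will be used, and the software is Stata and R. This stands: a standard survival routine would return the correct PFS and OS medians. The SAP also partly records completed work, so the edit may change no reported number. What remains is a stated definition that contradicts the named method.

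Four stronger readings are tempting, and the documents do not support them.
- **That wrong medians were produced.** Nothing points to a hand-built estimator.
- **That the bracket shortens drug survival or time to best response.** The first is sent to other methods. The second is defined in responders only, all of whom have the event, so the two medians coincide.
- **That the landmark denominator in SAP 8.2.3 ("the denominator will be all patients known to be alive at the selected time-points") shows the same error.** It concerns proportions, not medians, and it removes deaths, which pushes the result upward. It is a separate matter.
- **That the shortfall is very large.** Censoring spread evenly over 12 to 36 months would turn 24.8 months into 19.5. However, both documents follow each patient for a fixed period, and that pattern appears nowhere in them.

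On drug survival, Protocol 9.7 allows the SAP to modify its plans, so the departure is not a breach. It is still unexplained.

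**Conclusion.** The point holds as a definition to correct. The wording in SAP 8.1.3 is not the Kaplan-Meier median and can only give an equal or shorter value for PFS, OS and duration of response. The direction follows from algebra and needs no assumption about the shape of the curves. The size rests on assumed exponential times, a true median of 20 to 25 months and assumed loss rates: zero without early censoring, about 3% to 8% at 5% to 10% per year, and about 13% to 15% at 20%. Under the 2-year analysis the sharper effect is a reported median where Kaplan-Meier would give *not reached*, and this is most likely when the true median lies near or beyond 24 months.

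For time to discontinuation and time to dose reduction, the SAP departs from the protocol's Kaplan-Meier analysis. For discontinuation, it omits patients still on treatment. That can matter more than the bracket.

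**What to change.** 1. In SAP 8.1.3, delete the bracketed explanation and replace *may be used* with *will be used*.
2. State that Kaplan-Meier applies to OS, PFS, duration of response, time to dose reduction and time to discontinuation. The last two should include all treated patients, with those without the event censored at a stated date. Protocol 9.7 gives no censoring date for these two, so the SAP needs one.
3. Define the median as the earliest time at which the Kaplan-Meier estimate is 0.5 or below, reported as *not reached* if it stays above 0.5, with a Brookmeyer-Crowley 95% interval.
4. Align section 6 (Secondary Objective 1), section 8.2.2 and the treatment-pattern row of the 8.2.9 table. If summaries among discontinuers are kept, label them as such and report them in addition.

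Items 1 and 3 cost one or two sentences. Items 2 and 4 change the method for two endpoints and need a short rerun, but no new data: start, dose-change and stop dates are already in the listed dataset.
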